7.3 Center Pooling

All investigators in the proposed study will conduct the study according to a common protocol and utilize the same Case Report Forms (CRFs) to collect study data. Throughout the trial, efforts will be made to ensure consistency among investigative sites in selection of patients and conduct of the study procedures. In addition, site study personnel training will be conducted prior to initiation of the study at each site and periodic monitoring will be conducted by Medtronic to ensure compliance with protocol requirements.

Data will be pooled across centers for all analyses. Each study center will stop enrollment in the Primary Cohort after they have identified a maximum of 8 subjects for whom at least 1 aDBS mode is acceptable and who enter the aDBS Evaluation Phase ($\sim 25\%$ of the total planned number of subjects). For the Directional Stimulation Cohort, each study center will stop enrollment after they have identified a maximum of 5 subjects for whom at least 1 aDBS mode is acceptable and who enter the aDBS Evaluation Phase. The actual number of subjects at a study center may be slightly larger due to the number of subjects that are enrolled prior to cessation of enrollment. This restriction is intended to reduce the possibility that the results from one study center will be overly influential in the overall study results.

Tests for a treatment difference in the Primary Cohort among centers are described in the supporting analyses of the objective sections below. When testing for differences between centers, centers with 5 or more FAS subjects will each be tested as separate centers. Those with less than 5 FAS subjects will be combined into a “pooled” pseudo-center to minimize the impact of small samples on the analysis. If the

¹ Fleiss JL. The statistical basis of meta-analysis. Stat Methods Med Res. 1993; 2(2):121-45.

pseudo-center contains more than 50% of the subjects, the centers will be combined into more than one pseudo-center. If more than one pseudo-center is needed, the centers will be randomly ordered and divided as near the midpoint as possible. If ambiguity between assigning a center to the first or second pseudo-center exists, the center will be assigned to the first pseudo-center.

7.4 Handling of Missing, Unused, and Spurious Data and Dropouts

All attempts will be made to minimize missing data. If 5% of the data or fewer are missing for the analysis in the Primary Cohort, no imputation will be used². Otherwise, if missing data are observed, multiple imputation will be used for the analysis of the primary and secondary objectives in the Primary Cohort, as described in the objective sections below. If an aDBS mode is not programmable to a subject, no imputation will occur for those subjects for that aDBS mode. No imputations will be performed for the Directional Stimulation Cohort.

Appropriate confidence limits will be computed to account for the multiple imputations.^{3,4} A Complete-Case Analysis Set and As-Treated Analysis Set will be used for sensitivity analyses of the primary and secondary objective analyses in the Primary Cohort.

7.5 Adjustments for Multiple Comparisons

In the Primary Cohort, the familywise error rate will be controlled using one-sided tests with an overall alpha-level of 0.025. Each primary hypothesis (one for each aDBS mode) will be assigned a Bonferroni corrected alpha (0.0125) for the respective primary hypothesis (0.025/2). The primary hypothesis will serve as a gatekeeper for the secondary hypothesis within each mode. No adjustments of multiple comparisons are needed for the Directional Stimulation Cohort as no hypothesis testing will be conducted.

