13.5.4. Sample Size justification

The sample size was estimated using a one-sided test (alpha=0.0125) for one mean (PASS 2011 module Tests for One Mean) to compare the difference in aDBS TEED to cDBS TEED of 22 and a standard deviation of 35, a minimum of 36 subjects achieves at least 90% power.

Based on the registry data and the bench testing, a conservative estimate based on the first quartile of TEED data for initial devices in the registry, TEED is expected to decrease 35 and 22 units for aDBS single threshold mode and aDBS dual threshold mode, respectively. A SD of 36 results in a medium to large effect size of 0.629.

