7.9.2.2 Hypothesis

Two secondary hypotheses are being tested using independent gatekeeper procedures to control the alpha-level as described in section 7.9.1.1. The two secondary alternative hypotheses comparing aDBS (Evaluation Phase) to cDBS (Baseline Phase) separately, are:

- H_{12} : Mean Difference between aDBS dual threshold (Evaluation Phase) minus cDBS (Baseline Phase) for TEED < 0
- H_{22} : Mean Difference between aDBS single threshold (Evaluation Phase) minus cDBS (Baseline Phase) for TEED < 0

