7.9.2.4 Sample Size justification

The sample size was estimated using a one-sided test ($\alpha=0.0125$) for one mean (PASS 2011 module Tests for One Mean) to compare the difference in aDBS TEED to cDBS TEED of 22 and a standard deviation of 35, a minimum of 36 subjects achieves at least 90% power.

Based on the registry data and the bench testing, a conservative estimate based on the first quartile of TEED data for initial devices in the registry, TEED is expected to decrease 35 and 22 units for aDBS single threshold mode and aDBS dual threshold mode, respectively. A SD of 36 results in a medium to large effect size of 0.629.

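### The multiplicity rule is valid but leaves 0.0125 unused once one mode has passed both its tests; passing it to the other mode would raise Dual Threshold TEED power by about 4.5 points at 36 subjects per mode, and by 7 to 8 at 24 to 30

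*SAP*

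**What the plan says.** SAP 7.5 and Protocol 13.2.3 state that "the familywise error rate will be controlled using one-sided tests with an overall alpha-level of 0.025". Each mode's primary hypothesis gets 0.0125, and "The primary hypothesis will serve as a gatekeeper for the secondary hypothesis within each mode". SAP 7.9.2.2 (likewise Protocol 13.5.2) adds: "Two secondary hypotheses are being tested using independent gatekeeper procedures to control the alpha-level". Neither document moves alpha from one mode to the other. The only other use of 0.025 is the pooled-mode test in SAP 7.2.1 and Protocol 13.2.9, which is a separate branch.

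The fixed level recurs in the primary pass rule (SAP 7.9.1.4, Protocol 13.4.4), which requires p below 0.0125. Under imputation, the test compares a 97.5% lower confidence limit with 50% (SAP 7.9.1.5, Protocol 13.4.5).

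The TEED sample size was also set at 0.0125, with this claim: "TEED of 22 and a standard deviation of 35, a minimum of 36 subjects achieves at least 90% power". The two modes are not expected to do equally well: "TEED is expected to decrease 35 and 22 units for aDBS single threshold mode and aDBS dual threshold mode, respectively".

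**The concern.** The plan runs two closed chains: Dual diary then Dual TEED, and Single diary then Single TEED, each at 0.0125. Once both hypotheses in a chain are rejected, that chain has no further use for its alpha. A Bonferroni-based graphical procedure would pass it to the other chain within the same familywise limit.

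At stake is mainly the weaker claim. Single Threshold is expected to save more energy, so its chain should usually finish and release its 0.0125. Dual Threshold TEED, with the smaller expected drop, could then usually be tested at 0.025.

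This matters most when a mode has fewer than 36 subjects, which the plan allows. The 36 completers are subjects with at least one acceptable mode, so they are a total and not a count per mode. The plan secures only 8 per mode, and the first-period and pooling branch opens only below 24. Separate-mode tests on 24 to 35 subjects can therefore occur.

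**Working it through.** **Inputs.** One-sided alpha 0.0125 per mode, TEED drop 22 (Dual) and 35 (Single), SD 35 (SAP 7.9.2.4); 85% responders against 50%, n = 36 (SAP 6). Assumptions of this check, not of the plan: SD 35 for Single as well, equal n in both modes, independent modes, and diary and TEED results independent within a mode.

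**1. The plan's own figures.** TEED power is P(T > t(1−α; n−1)), with T noncentral t, n−1 degrees of freedom and noncentrality (22/35)√n. At n = 36 the noncentrality is 3.77; power is 91.8% at 0.0125 (normal approximation 93.7%) and 95.6% at 0.025. The plan's claim is reproduced. The SAP also says "A SD of 36 results in a medium to large effect size of 0.629"; 22/35 = 0.629 but 22/36 = 0.611. With SD 36 the power is 90.2%, so the claim holds either way. The primary test needs at least 26 of 36 responders (exact level 0.0057, power 98.6%), which also meets its 90% target.

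**2. Is recycling valid?** The rule: if one mode's diary and TEED hypotheses are both rejected at 0.0125, test the other mode's diary hypothesis and then its TEED hypothesis at 0.025.
- If one mode contains no true null, the other mode's ordered sequence is tested at 0.025 at most.
- If both modes contain a true null, neither can receive 0.025 until the other's true null has been rejected at 0.0125. The chance of any false rejection is at most 0.0125 + 0.0125 = 0.025.

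This holds for any correlation between modes. Every rejection under the present rule is kept. Simulation (200,000 trials per scenario, n = 36, correlation 0 and 0.5) gave a maximum familywise rate of about 0.0248.

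**3. Size of the gain.** Let G be the diary power, D the Dual TEED power, and W the chance that Single passes both tests at 0.0125. Subscripts 1 and 2 mark alpha 0.0125 and 0.025.
- Present rule: G₁ × D₁
- With recycling: W × G₂ × D₂ + (1 − W) × G₁ × D₁

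| n per mode | Diary cut-off at 0.0125 / 0.025 | G₁ / G₂ | D₁ / D₂ | W | Present | Recycled |
|---|---|---|---|---|---|---|
| 36 | 26 / 25 | 0.9863 / 0.9952 | 0.9181 / 0.9560 | 0.9861 | 90.6% | 95.1% |
| 30 | 22 / 21 | 0.9722 / 0.9903 | 0.8532 / 0.9142 | 0.9709 | 83.0% | 90.3% |
| 24 | 18 / 18 | 0.9428 / 0.9428 | 0.7479 / 0.8386 | 0.9346 | 70.5% | 78.5% |

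At n = 36, for example: 0.9861 × 0.9952 × 0.9560 + 0.0139 × 0.9055 = 0.9382 + 0.0126 = 0.9508.

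**4. How much is TEED, how much the diary cut-off.** At n = 30, keeping the diary cut-off at 22 gives 0.9709 × 0.9722 × 0.9142 + 0.0291 × 0.8295 = 0.887. About 5.7 of the 7.3 points come from the TEED test; the rest come from the lower diary cut-off. At 24 the cut-off does not move, so the whole gain is TEED.

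**5. Sensitivity to Single.** If the Single drop were also 22 at n = 36, W falls to 0.9055 and the result is 0.9055 × 0.9952 × 0.9560 + 0.0945 × 0.9055 = 0.947, a gain of 4.2 points. With Dual at 36 and Single at 16, W is about 73% and the gain about 3.3 points.

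**6. Actual error.** With only Dual TEED null, the error rises from 0.012 to 0.025. With only the Dual diary hypothesis null, it rises from 0.006 to 0.014–0.015. With all hypotheses null it stays at 0.011.

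**The case against.** The strongest reply is that nothing is broken. The present procedure is valid, TEED is secondary, trial success rests on the diary endpoint in either mode or the modes combined (SAP 7.2), and the TEED target is met at 36. A sponsor may deliberately keep two self-contained mode claims. All of that stands.

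It also stands that recycling has consequences. The rule is symmetric and reaches the second mode's diary test: a mode with 25 of 36 responders, a failure today, would pass because the other mode also saved energy. Actual error rises towards the limit in some configurations. A change to a principal feature needs an SAP amendment (SAP 7.11), and Protocol amendments go to ethics committees and, where required, regulators (Protocol 15.6). Only subjects are blinded, so a late change invites a charge that it was made with results in view. The documents do not show whether the data freeze has passed. The power figures use the t-test only, not the planned Wilcoxon fallback.

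A reader might infer more than the documents support:
- That familywise error is not controlled. It is.
- That TEED is underpowered as planned. At 36 per mode it is not.
- That the trial's success is in danger. The gain falls mainly on the second mode's claims.
- That the change has no downside, or concerns TEED alone. Neither is so, for the reasons above.

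What the reply does not remove is the unused 0.0125, or the loss below 90% gated power when a mode has clearly fewer than 36 subjects.

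**Conclusion.** The point holds as an efficiency improvement to a valid plan. The gain in gated Dual Threshold TEED power is about 4.5 points at 36 per mode, 7 at 30 (part of it from the relaxed diary cut-off) and 8 at 24. At 30 per mode it brings power back to about 90%; at 24 it does not. These sizes rest on the assumptions listed with the inputs. The gain is smaller if Single Threshold has few subjects or a smaller drop, and it is nil whenever Single fails either of its tests. Validity within 0.025 does not depend on those assumptions.

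**What to change.** Amend before the data freeze, and before anyone taking the decision has seen outcome data.

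- **SAP 7.5 and Protocol 13.2.3.** Add: *When the modes are tested separately, if both the primary and the secondary hypothesis of one mode are rejected at one-sided 0.0125, the primary and then the secondary hypothesis of the other mode are tested at one-sided 0.025. If the modes are pooled, the pooled test at 0.025 replaces the separate tests.* The pooled test itself is unchanged.
- **SAP 7.9.1.4 and Protocol 13.4.4.** Make the 0.0125 pass rule conditional in the same way; otherwise it contradicts the new sentence.
- **SAP 7.9.1.5 and Protocol 13.4.5.** State the confidence limit used under imputation as one-sided: 98.75% when alpha is 0.0125, 97.5% when it is 0.025. The distinction decides cases. The exact lower limit is the α quantile of Beta(x, n − x + 1); for 25 of 36 it is 51.9% at one-sided 97.5% but 49.5% at one-sided 98.75%.
- **SAP 7.9.2.2 and Protocol 13.5.2.** Stop describing the two gatekeeping procedures as independent.

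The cost is one SAP and one Protocol amendment with their reviews, and acceptance that the second mode's diary claim may be made at 0.025. No subjects are added and no present rejection is lost.

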7.6 Demographic and Other Baseline Characteristics

Demographics and baseline characteristics will be summarized for the AC, FAS, and DSCC analysis sets. This will at least include:

Baseline demographics:

- Age
- Sex
- Ethnicity
- Race

PD history:

² Buhi, E, Goodson, P, Neilands T. Out of Sight, Not Out of Mind: Strategies for Handling Missing Data. *Am J Health Behav.* 2008 Jan-Feb;32(1):83-92, doi: 10.5555/ajhb.2008.32.1.83.

³ Rubin, D. B. (1976). "Inference and Missing Data." *Biometrika* 63:581–592.

⁴ Rubin, D. B. (1987). *Multiple Imputation for Nonresponse in Surveys*. New York: John Wiley & Sons.

- PD duration
- Dyskinesia duration
- Location of dyskinesias
- Motor fluctuation duration
- Duration of L-DOPA treatment
- Duration of dopamine agonist treatment

7.7 Treatment Characteristics

Device data will be summarized as specified in Section 7.9.3.11.

7.8 Interim Analyses

No formal interim analysis is planned.

7.9 Evaluation of Objectives

7.9.1 Primary Objective

To demonstrate that the proportion of aDBS subjects with “On” time without troublesome dyskinesia during the Evaluation Phase exceeds a performance goal of 50%.

7.9.1.1 Hypothesis

Two hypotheses are being tested for the primary objective in order to compare each aDBS mode relative to cDBS at baseline, separately. The alternative hypotheses are:

- H_{11} : The proportion of subjects with “On” time without troublesome dyskinesia during aDBS dual threshold mode Evaluation Period exceeding threshold > 50%
- H_{21} : The proportion of subjects with “On” time without troublesome dyskinesia during aDBS single threshold mode Evaluation Period exceeding threshold > 50%

7.9.1.2 Endpoint definition

The primary endpoint is the proportion of aDBS subjects with “On” time without troublesome dyskinesia that exceed threshold. This endpoint will combine the diary categories of “On” time without dyskinesia and “On” time with non-troublesome dyskinesia. Since the device implant will occur outside of the study and the study requires participants to be stable on cDBS, the within-subject standard deviation of the change between cDBS and DBS in “On” time without troublesome dyskinesia will be used to establish a threshold for assessing the performance goal. The threshold will be set as 1 standard deviation. If the difference between aDBS and cDBS (aDBS-cDBS) for a subject is at least -1 standard deviation, the threshold will be met for the subject. Using this threshold, the proportion of subjects who exceed the threshold will be computed. The primary endpoint proportion of subjects above threshold will be compared to a performance goal of 50% using a binomial exact test. The lower bound of the 97.5%

confidence limit will also be presented. Data will be imputed as described in 7.4 prior to computing the mean “On” time without troublesome dyskinesia for all periods when using the FAS.

Rationale for endpoint

Continuous Deep Brain Stimulation is a proven FDA-approved therapy in the treatment of Parkinson’s disease symptoms. This study aims to show that aDBS is a viable optional feature that can provide similar benefit and safety to cDBS for some subjects. The primary endpoint for this study compares aDBS to cDBS directly for each subject to ensure some level of consistent comparability between cDBS and aDBS. The endpoint of PD Home Diary was chosen to determine the threshold of success as it is a measure of the subject response to DBS therapy over time, the aDBS algorithm will adapt the therapy over time, and the PD Home Diary has been used as an endpoint in previous DBS trials.

Rationale for 1 standard deviation threshold

A unit of one standard deviation was chosen as it is an acceptable amount of statistical variability in the PD Home Diary endpoint given the fluctuating nature of Parkinson’s disease and the percentiles of a normal distribution.

Rationale for 50% performance goal

A performance goal of 50% was chosen for this study in order to demonstrate that at least 50% of the subjects are able to achieve the threshold with 95% confidence demonstrating some level of efficacy.

7.9.1.3 Sample size justification

The sample size justification for the primary objective is provided in section 6.

7.9.1.4 Analysis methods

The primary analysis will use the FAS as described in section 7.1.3. The PD Home Diary will be collected for at least 3 consecutive days (24 hour “periods”) prior to each visit to evaluate the primary objective. Complete diary periods collected anytime during the cDBS Baseline period will be used for analysis as subjects should be on stable cDBS stimulation from enrollment through the end of this period. In the aDBS Evaluation Phase, diary periods will be defined starting with the first completed diary record which is no more than 14 days prior to the visit. If diary is collected more than 14 days prior to the visit, the diary may be used for analysis if there is no change in aDBS stimulation settings. Complete diary periods are defined as any diary period where at least 21 hours (defined as 42 30-minute records) of diary were completed during the 24-hour period, and only complete periods will be used for analysis. If the diary is collected for more than 3 complete periods, up to 7 which are closest to the visit will be used for the analysis, while if a subject has zero complete periods, their diary will be considered missing. Diaries with at least 1 complete period available will be used for analysis. Data from non-contiguous complete periods may be used in the analysis.

The change in daily “On” time without troublesome dyskinesia from cDBS to aDBS will be computed for each subject. The overall standard deviation of the change will be computed for the FAS. The threshold will be set as 1 standard deviation. If the difference between aDBS and cDBS (aDBS-cDBS) for each subject is at least -1 standard deviation, the threshold will be met for the subject. Using this threshold, the proportion of subjects who exceed the threshold will be computed. The proportion with “On” time without troublesome dyskinesia during the respective aDBS Evaluation Period that exceed the threshold will be compared to the performance goal of 50% for each aDBS mode separately using a binomial exact test. The objective will be considered passed if the p-value is less than 0.0125. The lower bound of the 97.5% confidence interval will also be presented.

7.9.1.5 Handling of missing data

All attempts will be made to minimize missing data. If 5% of the data or fewer are missing (as defined in section 7.9.1.4) for the analysis, no imputation will be used and the data will be analyzed as specified in the previous section. Otherwise, if missing data are observed, multiple imputation will be used for the analysis of the key primary objective.

Prior to the MI, the distribution of the continuous variables will be assessed for normality (using the Shapiro-Wilk test) to determine whether regression ($P \geq 0.05$) or predictive mean matching ($P < 0.05$) multiple imputation will be used for each variable. First, multiple imputation will be applied to impute missing values in continuous hours of “On” time without troublesome dyskinesia for each mode separately (aDBS single threshold, aDBS dual threshold). The model variables in the MI analysis may include, as appropriate:

- target site (STN or GPi)
- cDBS hours of “On” time without troublesome dyskinesia
- Age
- Gender
- Center
- PD duration

Variables will be ordered in the model based on the level of missingness (from least to most missing) and in the order specified above when the missingness is equal for 2 or more variables.

The fully conditional specification (FCS) method within SAS (version 9.4 or higher) with 5 repetitions and 100 burn-in iterations will be used for imputation. No limits will be defined for imputed values.

Following imputation, the “On” time without troublesome dyskinesia will be assessed against the “On” time threshold, and the estimate for the proportion of subjects meeting threshold will be determined for each imputation and combined using MI analysis methods. The lower bound of the 97.5% confidence limit will be determined using the MI Clopper-Pearson mean success approach⁵. In addition, the objective will be tested by comparing the lower bound of the 97.5% confidence limit to 50% for each imputation, and the overall p-value will be computed as the median of the p-values from the multiply imputed datasets.⁶

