Since the device implant will occur outside of the study and the study requires participants to be stable on cDBS prior to enrollment, the standard deviation of the change from cDBS to aDBS in “On” time

without troublesome dyskinesia will be used to establish a threshold for assessing the performance goal. The threshold will be set as 1 standard deviation. If the difference between aDBS and cDBS (aDBS-cDBS) for a subject is at least -1 standard deviation, the threshold will be met for the subject. Using this threshold, the proportion of subjects who exceed the threshold will be computed.

The sample size was estimated using a binomial distribution for a one-sided exact test (alpha=0.0125) for a proportion (PASS 2011 module Tests for One Proportion [Differences]) to compare to a performance goal of 50%. Assuming the alternative hypothesis of 85% of subjects exceeding the threshold, a minimum of 36 subjects achieves at least 90% power to reject a performance goal of 50%.

Simulations have shown that this sample size is sufficient to cover possible deviations from normality such as a uniform distribution. The threshold criterion will remain the same as the standard deviation is robust to moderate departures from normality.

Sample size in the Primary Cohort may be increased to a maximum of 55 subjects for whom at least 1 aDBS mode is acceptable and who enter the aDBS Evaluation Phase to obtain at least 8 subjects per aDBS mode and 8 subjects per target site (Subthalamic Nucleus [STN]/ Globus Pallidus [GPi]). Criteria for increasing sample size is described in section 7.2.1.

For the safety analyses, a minimum of 30 subjects followed for approximately 30 days with aDBS out-of-clinic in the subjects' real-world environments provides at least 95% probability that all events with a true event rate of at least 10% would be reported at least once.

It is estimated that approximately 70-100 subjects implanted with a commercially available Medtronic DBS system with Percept PC INS will be enrolled in the study to obtain 40 subjects for whom at least 1 aDBS mode is acceptable and who enter the aDBS Evaluation Phase. Accounting for a 10% dropout during the aDBS Evaluation Phase, a minimum of 36 subjects (at least 8 per brain target site (STN/GPi) and 8 per aDBS mode) will complete the aDBS Evaluation phase.

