7.9.2.6 Handling of missing data

All attempts will be made to minimize missing data. If 5% of the data or fewer are missing for the analysis, no imputation will be used and the data will be analyzed as specified in the previous section. Otherwise, if missing data are observed, multiple imputation will be used for the analysis of the secondary objective.

Prior to the MI, the distribution of the continuous variables will be assessed for normality (using the Shapiro-Wilk test) to determine whether regression ($P \geq 0.05$) or predictive mean matching ($P < 0.05$) multiple imputation will be used for each variable. First, multiple imputation will be applied to impute missing values in TEED for each mode separately (aDBS single threshold, aDBS dual threshold). The model variables to include and methods used for the MI analysis are described in Section 7.9.1.5, except that a variable for cDBS TEED will be included in the model instead of cDBS hours of "On" time without troublesome dyskinesia. The FCS method within SAS (version 9.4 or higher) with 5 repetitions and 100 burn-in iterations will be used for imputation. No limits will be defined for imputed values.

Following imputation, the mean and standard error of the change in TEED will be determined for each imputation using Proc UNIVARIATE:

Proc MIANALYZE will be used to combine the summary statistics and to test the change in TEED with a t-statistic comparing the value to no change.

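### Imputing each aDBS mode on its own leaves out the same subject's observed On time in the other mode: a small, conditional upward bias that a wording change removes

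*SAP*

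**What the plan says.** SAP 7.9.1.5 sets a trigger: "If 5% of the data or fewer are missing (as defined in section 7.9.1.4) for the analysis, no imputation will be used". Above it, continuous hours of On time are imputed "for each mode separately (aDBS single threshold, aDBS dual threshold"), by FCS with 5 imputations. The variables that may enter are target site, cDBS hours, age, gender, center and PD duration. Protocol 13.4.5 names only target site and cDBS hours. Neither list contains On time in the other aDBS mode.

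SAP 7.9.2.6 handles the secondary endpoint in the same way ("impute missing values in TEED for each mode separately"), with cDBS TEED in place of cDBS hours.

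SAP 7.4 rules out imputing a mode that could not be programmed. SAP 7.9.1.6 plans complete-case and as-treated sensitivity analyses. On loss, SAP section 6 says: "Accounting for a 10% dropout during the aDBS Evaluation Phase, a minimum of 36 subjects".

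**The concern.** A subject randomised to both modes is scheduled to complete two aDBS diaries, with evaluation visits 30 to 45 days apart (Protocol Table 4). If the second is missing, the first remains as direct evidence of how that person responds to aDBS. The planned model does not use it. A subject who did badly in the first mode is imputed like any other subject with the same cDBS hours and covariates.

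This matters if a poor first month makes a missing second month more likely. Missingness then depends on a variable that was observed but is not in the model, so the imputed pass rate for those subjects is too high and the primary proportion moves towards success. The complete-case analysis does not protect against this, because it omits the same subjects and also does not use their first-mode value.

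**Working it through.** **Inputs from the documents.** One-sided alpha 0.0125 per mode (SAP 7.5); performance goal 50%, alternative 85%, 36 completers, 10% dropout (SAP section 6); 5% trigger and 5 imputations (SAP 7.9.1.5); randomised mode order (Protocol 9.9.3).

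**Inputs assumed, because the documents give none.** Correlation of cDBS with aDBS On time 0.5 to 0.6; correlation between modes 0.6 to 0.85; normal data; all 40 entrants assigned to both modes. Wider ranges are marked where used.

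**1. The plan's own figure.** SAP section 6 states that "a minimum of 36 subjects achieves at least 90% power to reject a performance goal of 50"%. The smallest k with P(X ≥ k | 36, 0.5) < 0.0125 is k = 26, with tail 0.0057. P(X ≥ 26 | 36, 0.85) = 0.986. The claim holds as a lower bound. Entrants: 36 / (1 − 0.10) = 40, where 28 passes (70%) are needed.

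**2. How many missing values could the other mode inform?** Ten per cent of 40 is 4 leavers over the whole two-period phase. A period-1 leaver has no aDBS diary in either mode. A period-2 leaver lacks one mode, and random order makes it either mode with probability ½. Per mode, 2/40 = 5% is not imputed and 3/40 = 7.5% is. Reading the 5% rule by mode, with no other missing diaries:

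| Leavers, period 1 / period 2 | Expected missing per mode | Of these, other mode observed | Chance a given mode exceeds 5% |
|---|---|---|---|
| 2 / 2 | 2 + 1 = 3 | 1 | P(Bin(2, ½) ≥ 1) = 75% |
| 1 / 3 | 1 + 1.5 = 2.5 | 1.5 | P(Bin(3, ½) ≥ 2) = 50% |
| 0 / 4 | 0 + 2 = 2 | 2 | P(Bin(4, ½) ≥ 3) = 31% |

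**3. Bias in the pass proportion.** Simulation: change = aDBS − cDBS; pass if change ≥ −1 SD, with the SD recomputed in each completed data set; regression imputation with 5 imputations; mean change zero; imputation applied whenever a value is missing. The predictors are cDBS hours alone, or cDBS hours plus the other mode.

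- *4 leavers split across periods, period-2 loss related to a poor first mode:* bias +0.2 to +1.0 points with the other mode omitted, about 0 to +0.2 with it included. Root mean squared error is equal or lower with it.
- *Missing completely at random, 10% or 20% missing in one mode (wider ranges: cDBS correlation 0.5 to 0.8, between modes 0.6 to 0.9):* bias −0.2 to +0.1 points when omitted. At 10% missing, the error falls from 2.16 to 1.90 points at correlations 0.6 (cDBS) and 0.8 (between modes), but only from 2.17 to 2.12 when both are 0.8.
- *Stress case, 10% missing in one mode, every missing subject observed in the other, loss tied to a poor result there (same wider ranges):* +0.7 to +2.6 points omitted. At 20% missing, +1.4 to +5.2. With the other mode included, bias is between −0.2 and +0.4 in all these scenarios.
- *Extreme case, the 4 worst in the other mode always missing (residual correlation 0.3 to 0.8):* +1.2 to +3.7 points omitted, at most 0.3 included.

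Cross-check: the extreme case has 4 such subjects in one mode, and step 2 gives 1 to 1.5 for the first two splits. Scaling, 1.2 × 1/4 = 0.3 and 3.7 × 1.5/4 = 1.4, close to the first result.

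**4. Effect on the decision.** With zero mean change and normality, the pass probability is Φ(1) = 0.841 and P(X ≥ 28 | 40, 0.841) is about 0.993. The simulations gave 99 to 100% under either model. With non-zero change, the stress setting (4 missing in one mode, all observed in the other; correlations 0.6 and 0.8) gave these chances of passing:

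| Mean change; loss pattern | Full data | Other mode omitted | Other mode included |
|---|---|---|---|
| −0.6 SD; 4 worst missing | 31% | 43% | 32% |
| −0.6 SD; softer dependence | 34% | 41% | 34% |
| −1 SD (null boundary); softer dependence | 1.3% | 1.9% | 1.1% |

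These are upper-end figures, because dropout at the planned rate would leave fewer such subjects per mode.

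**The case against.** The strongest case against is about size. The planned 10% covers both periods, so few missing values in either mode come with the other mode observed; step 2 shows 1 to 2. If all four leave in period 2, the expected loss per mode sits exactly at 5%, where nothing is imputed. With zero mean change the decision does not move. cDBS hours are already in the model and form half of the change score. All of this stands and sets the size of the point.

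Two further arguments carry less weight. The SAP list is permissive, and the example imputation code mentioned in its version history is not visible in the public copy, so the code may include the other mode. But the other mode is not among the listed options, and imputing each mode separately points away from it. Second, if carryover is found (SAP 7.9.1.6) or the first-period analysis for pooling modes applies (SAP 7.2.1), only first-period data are used and the issue disappears. That narrows the point without removing it.

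A reader might infer more than the documents support:

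- that the other mode is the strongest predictor available. No correlations are given, and the gain under random loss nearly vanishes when the cDBS correlation is as high;
- that imputed results are biased upward in general. Under random loss the bias is about zero;
- that imputation is the likely route for the primary test. It depends on how leavers split between periods and on the number of blank diaries, for which no rate is given;
- that TEED is affected to the same degree. aDBS TEED comes from device recordings (SAP 7.9.2.3.2), and no effect was computed.

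**Conclusion.** The point holds in a limited form. The plan leaves an observed, likely useful predictor out of the imputation for randomised subjects who lose one period. The consequence is an upward bias of roughly 0.2 to 1 percentage point at the planned loss, and only if poor results in the first mode make missing data in the second more likely. It is larger only if more second-period data are missing or the dependence is extreme. It could affect the conclusion if aDBS is moderately worse than cDBS and such losses are heavier than planned dropout implies.

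This rests on assumed correlations and an assumed loss mechanism, and on regression imputation; predictive mean matching, the SAP's alternative for non-normal data, was not simulated. Nothing found suggests that adding the predictor does harm. It is an optional refinement.

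**What to change.** In SAP 7.9.1.5 and Protocol 13.4.5, state that for subjects assigned to both modes, Dual and Single On time are imputed in one FCS model, each with the other mode's value as a predictor alongside cDBS hours, target site and period or sequence. Period or sequence is needed because a subject's two values come from different periods. Keep the current model for single-mode subjects and for subjects with no aDBS diary, and keep the rule against imputing a mode that was never programmed. The same wording can go into SAP 7.9.2.6 and Protocol 13.5.6 for TEED, for consistency.

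The cost is a few sentences and a few lines of code, with no new data. The downsides are a separate imputation step for single-mode subjects and one or two more parameters in a small-sample model. The change cannot help subjects who leave before any aDBS diary.
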